The emotional reactivity computerized task was developed specifically for our protocol with OpenSesame® software. The task looks like a type of stroop task. Instructions are to identify as soon as possible the ink color of the word on the screen matches the meaning of the word, in doing as less as possible mistake. We ask to the participants to press a specific button on the keyboard in the case of the ink color of the word matches the meaning of the word and to press on another button on the keyboard if they don't. We developed the task in 3 similarly but not identical versions with the aim of randomly testing the 3 versions on each participant. Each version lasts 12 minutes and has some particularities such as the colors of the words. We generated 3 versions of the task in the aim to limit the classical habituation effect in participants. Each version is made of 6 blocs in 20 trials that is aiming at progressively increasing the stress level because of an increase of the mental load. Bloc 1¹ and bloc 2 are associated with a low stress, bloc 4 and bloc 5 are associated with a moderate stress and bloc 5 and bloc 6 are associated with a high stress. The increase of the mental load is permitted by slowly decreasing the word presentation time, by putting feed-back, instruction switches, time constraints and lastly, by the necessity to do a dual task.

STAI Y-A / PANAS / CES-D / PSS / CFS / SWLS / ICQ-18	ECG/EGG/EEG/ GSR/PPG/Emwave/ respiratory belt positioning	Resting period (30 minutes, seated, eyes closed)	Reactivity period (during the task, seated)	VAS	Recovery period (30 minutes, seated, eyes closed)
--	---	--	---	-----	---

3h30

The period (24 days) between the first session and the second session (T1-T2) will be considered as the control period. The larger BFB effects than the unspecific effects related to the spontaneous physiological and emotional variations will be verified through the control period. We will measure the parameters of interest before (T1) and at the end of the control period (T2). During the period, the participants will have to answer to online questionnaires (SSQ6, MAIA-2, STAI Y-B, Brief-Cope, BFI-N, CTQ) aiming to examine the psychological profile (social support, interceptive sensitivity, trait anxiety, style of coping, early life events).

The second session (T2), T1 + 24 days, will be similar of the first session. We will use the same questionnaires and will record the same electrophysiological parameters. At the end of the

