[figure not shown]
¹ The bloc 1 will not be included in the final statistical analysis because is considered as a training bloc. This choice in accordance to the potential biases related to the increase of the sympathetic activity at the beginning of the task caused by a simple moving to action following the resting period.

second session, a short training session of the biofeedback [BFB] technique will be done and the software using for the biofeedback training will be supplied to each participant included in the experimental group to allowed to us to practice BFB by their self at home. The installation of the program and the explanations needed for using it, will be done during the second session (T2). The BFB software (Emwave Pro®) includes a photoplethysmography sensor that can be positioned on the earlobe. The participants will have to practice the biofeedback technique the next 24 days (3X5 min/day).

The period (24 days) between the second session and the third session (T2-T3) will be considered as the intervention period. At the end of the second session (T2), the participants will be separated into two inter-subject groups: an experimental group performing BFB technique (3X5 min per day) in the intervention period (T2-T3) and a control group not performing a specific exercise in the intervention period (T2-T3). The first 40 participants (20 IBS / 20 PNES) will be included into the experimental group (BFB training) whereas the last 10 participants (5 IBS / 5 PNES) will be included into the control group (no training). The participants won't be informed of the condition to which they belong. We will measure the parameters of interest before (T2) and at the end of the intervention period (T3). During the intervention period, all the participants will have to answer to online questionnaires (BVAQ-B, LES, DHS) aiming to examine the psychological profile (alexithymia, traumatic events).

The third session (T3), T2 + 24 days, will be similar of the two previous sessions. We will use the same questionnaires and will record the same electrophysiological parameters. Finally, a debriefing will be done at the end of the session for each participant. The session will be considered as the end of the study visit.

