- SDNN (standard deviation of all NN intervals) temporal-domain parameter
- EDR (ECG-derived-respiration)

GSR (tonic GSR / phasic GSR):

- SCR frequency: number of the spontaneous galvanic skin responses by periods
- SCR amplitude: amplitude of the spontaneous galvanic skin responses by periods
- Integrated skin conductance responses [ISCR]: area of the galvanic skin responses identified on the signal

PPG:

- Pulsatility index variation (PI): Transit time flow

Breathing belt:

- Breathing rate by cycles per minute

EGG:

- Dominant power
- Total power [0-0.15 Hertz]
- Slow-waves frequency per minute

EEG:

- Spontaneous brain rhythms: spectral power of the 0-30 Hertz band

Physiological adaptation to the aversive situation (emotional reactivity task):

HRV, GSR and PPG differences will be calculated to measure the physiological changes causing by the task compared to the resting and the recovery periods. The differences will be calculated as follows:

- Physiological reactivity during the task compared to the resting period (Δ = reactivity HRV – resting HRV / Δ = reactivity GSR – resting GSR / Δ = reactivity PPG – resting PPG)
- Physiological recovery following the task (Δ = recovery HRV – reactivity HRV / Δ = recovery GSR – reactivity GSR / Δ = recovery PPG – reactivity PPG)

- Physiological recovery following the task compared to the resting period (Δ = recovery HRV – resting HRV / Δ = recovery GSR – resting GSR / Δ = recovery PPG – resting PPG)

Psychological variables:

- Alexithymia score (BVAQ-B)
- Neuroticism score (BFI-N)
- Trait anxiety score (STAI Y-B)
- Style of coping (Brief Cope)
- Positive affectivity score (PANAS)
- State anxiety score (STAI Y-A)
- Depressive symptoms score (CES-D)
- Perceived-stress level (PSS)
- Coping flexibility + metacoping scores (CFS + VAS)
- Acceptance score (ICQ-18)
- Social support score (SSQ6)
- Interceptive sensitivity score (MAIA-2)
- Life satisfaction score (SWLS)
- Negative impact scores (LES)
- Frequency, severity and intensity scores (DHS)
- Abuse scores (CTQ)

Statistical analyses

All statistical analyses will be performed using IBM SPSS Statistics®, R software® and JASP®. The alpha value for statistical significance will set at $p<0.05$.

Analyses of the scores collected will be done in several stages:

- Highlighting outlier participants to exclude from our statistical analysis.
- All the conditions for application of statistical tests will be verified.

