- In the case of a failure to respect the conditions for parametric test application, we would make a data transformation to jointly improve normality and homogeneity residues. If the normality is failed and the homogeneity is respected, we would execute non-parametric tests.
- Analysis will be done on the subjects included. Analysis concerning the reactivity period (during the task) will be performed on the all blocs excepted the bloc 1².
- Main and secondary judgment criterions analysis will be performed by parametric tests or by non-parametric tests depending on the conditions for application:

• *Analyse A:*

- An ANOVA to repeated measurement with an intra factor (measurement time: T1 / T2 / T3) and an inter factor (group: experimental / control) on the physiological and psychological data collected.
- Student's test for independent samples will be performed on the psychological scores collected in the second session (T2) to account for the initial level of psychological states between the 2 groups.

² The bloc 1 will not be included in the final statistical analysis because is considered as a training bloc. This choice in accordance to the potential biases related to the increase of the sympathetic activity at the beginning of the task caused by a simple moving to action following the resting period.

- Contrasts will then be made by group on the scores in order to specify the effect of the condition on the physiological and psychological data.
- *Analyse B:*
 - K means non-hierarchical clustering will be performed with K = 2. To categorise participants depending on their resting neurovegetative profile (low vagal tone / high vagal tone) and on their dynamical neurovegetative profile (low vagal flexibility / high vagal flexibility), two K means non-hierarchical clustering will be performed with K = 2. One with HF or RMSSD and one with Δ HF or Δ RMSSD.
 - Student's test for independent samples (dysfunctional neurovegetative profile / functional neurovegetative profile) will be performed on the psychological vulnerability (trait scores) collected.
- *Analyse C:*
 - An ANOVA to repeated measurement with an intra factor (measurement time: T2 / T3) and an inter factor (neurovegetative profile: dysfunctional profile / functional profile) on the physiological and psychological data collected only into the experimental group performing the BFB technique.
- *Correlational analysis:*

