 - Regressions or the Pearson correlations will be performed in order to measure the inter-signal correlation (ECG-EGG-EEG)
 - Regressions or the Pearson correlations will be performed in order to test our hypothesis about the HF/RMSSD related to the "low vagal tone" profile will be more correlated to Δ HF/RMSSD related to the "low vagal flexibility" profile than to Δ HF/RMSSD related to the "high vagal flexibility" profile. As the same as HF/RMSSD related to the "high vagal tone" profile will be more correlated to Δ HF/RMSSD related to the "high vagal flexibility" profile than to Δ HF/RMSSD related to the "low vagal flexibility" profile

Additional analyses

- We will control the age effect and the gender effect.
- Some additional statistical analyses will be exploratory: stability of the resting and the dynamical neurovegetative endophenotypes before the control period (T1) and at the end of the control period (T2).
- Correlation between the LF 0.1Hz and the clinical outcomes.
- To confirm the physiological effects of the BFB (BFB vs pseudo-BFB) on the flexibility of the electrophysiological coupling concerning the brain-visceral axis.

Sample

Power analysis (G * Power; Faul et al., 2007) was performed to determine a priori the sample size needed for this study. The power analysis, for an ANOVA (repeated measures, within-between factors), was performed for an effect size (η_p^2) of .12 with a power of .95 on the main judgment criterion (HRV – vagal tone HF) and reported a necessary sample of at least 22 participants (Kudo et al., 2014; Paul & Garg, 2012; Wells et al., 2012). We decided to include at least 25 IBS patients SII (20 test & 5 control) and 22 PNES patients (20 test & 5 control) in accordance with the possible inclusion rate and the duration of the study.

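### Analysis A tests biofeedback through a 2-df group × time interaction although T1 and T2 are both pre-treatment; a named 1-df contrast of T3 against the two baselines would usually be more powerful

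*Combined protocol and SAP*

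**What the plan says.** Under Statistical analyses, Analyse A, the plan specifies a repeated-measures ANOVA with a three-level within-subject factor ("measurement time: T1 / T2 / T3") and a two-level between-subject factor (experimental or control), applied to physiological and psychological outcomes. It adds a t-test between groups at T2, on psychological scores only, and follow-up contrasts made by group. No between-group contrast of T3 against baseline is named, and no model uses T1 and T2 together as baseline.

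Part I (Study protocol) makes T1–T2 a control period without BFB for everyone. Training and software are given at the end of the T2 session. The protocol gives T1–T2 a purpose: the excess of BFB effects over spontaneous variation "will be verified through the control period". The first 40 participants form the experimental group, "whereas the last 10 participants (5 IBS / 5 PNES) will be included into the control group".

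The Sample section bases its sample size on the within-between form of the repeated-measures ANOVA. For the main criterion, HF, the calculation "was performed for an effect size (η_p^2) of .12 with a power of .95". As its result, the section states that the calculation "reported a necessary sample of at least 22 participants". The significance level is .05: "The alpha value for statistical significance will set at $p<0.05".

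**The concern.** If BFB can act only at T3, the expected difference between groups follows the pattern (0, 0, d) over T1, T2 and T3. A 2-df interaction test also looks for group differences in the T1–T2 change, where BFB can produce none. That direction adds a degree of freedom to the numerator and no signal. A single contrast aimed at T3 against the pre-BFB sessions puts all the signal on 1 df.

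The control arm has 10 people, so its mean dominates the error of the BFB estimate. The loss applies to every outcome measured at all three sessions. The sample-size statement covers HF only; no power is given for the many other physiological and psychological outcomes in Analysis A, whose effects may be smaller. Leaving the contrast unnamed also leaves open which comparison will be reported as the BFB effect.

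**Working it through.** **Inputs from the documents.** Alpha .05; partial eta squared .12; power .95; N = 22; three sessions; groups of 40 and 10. **Assumptions.** Correlation r between sessions, the effect d at T3 in SD units, and no dropout; the documents give none of these.

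**1. The plan's own figure.** f² = .12/.88 = .1364. For the interaction with 2 groups and 3 sessions, λ = f² × N × 3/(1 − r), with df 2 and 2(N − 2). At r = .5 and N = 22, λ = .1364 × 22 × 3/.5 = 18.0 and power is .964. The smallest N reaching .95 is 21, or 22 with equal groups. The stated figure therefore reproduces for this 3-level interaction at r = .5.

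**2. Formulas for 40 against 10.** n₁n₂/N = 400/50 = 8. Under equal correlation:

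- 2-df interaction: λ = 8 × (2/3) × d²/(1 − r), df 2 and 96.
- T3 − T2 change: error variance 2(1 − r), df 1 and 48.
- T3 minus mean of T1 and T2: error variance 1.5(1 − r), df 1 and 48.
- ANCOVA of T3 on T2: error variance 1 − r², df 1 and 47.
- ANCOVA of T3 on T1 and T2: error variance 1 − 2r²/(1 + r), df 1 and 46.

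For the 1-df tests, λ = 8d²/(error variance). At d = .8 and r = .5, the interaction has λ = 8 × .6667 × .64/.5 = 6.83 and the T3-minus-mean contrast has λ = 8 × .64/.75 = 6.83. The two are identical, so the planned test loses only through the second numerator df.

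**3. Power (%), noncentral F, equal correlation.**

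| d | r | 2-df interaction | T3 − mean(T1,T2) | gain | ANCOVA on T1, T2 | gain |
|---|---|---|---|---|---|---|
| .5 | .5 | 28.2 | 36.0 | 7.8 | 39.6 | 11.4 |
| .5 | .7 | 44.3 | 54.2 | 9.9 | 56.7 | 12.3 |
| .5 | .8 | 61.8 | 71.6 | 9.8 | 73.1 | 11.3 |
| .8 | .5 | 62.9 | 72.6 | 9.7 | 77.4 | 14.5 |
| .8 | .7 | 85.4 | 91.1 | 5.7 | 92.6 | 7.2 |
| .8 | .8 | 96.2 | 98.2 | 1.9 | 98.5 | 2.2 |

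**4. At the plan's effect.** With 11 per group, n₁n₂/N = 121/22 = 5.5. Then λ = 18.0 gives d² = 18 × .5/(5.5 × 2/3) = 2.455, so d = 1.57. With 40 against 10, power is 99.7% (interaction), 99.9% (contrast) and 99.96% (ANCOVA), a gain under 0.5 points. If .12 is instead read as the ordinary ANOVA-table value, λ = f² × df₂ = .1364 × 40 = 5.45 and d = .86. The three powers are then 69.9, 78.8 and 83.3%.

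**5. How much is due to T1.** At d = .8, ANCOVA on T2 alone has power 72.6, 87.4 and 95.9% at r = .5, .7 and .8. Adding T1 gives 77.4, 92.6 and 98.5%, so T1 itself is worth about 3 to 5 points there.

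**6. If correlation decays with time (AR(1), d = .8).** ANCOVA on T2 alone and on both sessions have the same power (.725 at r = .5; .873 at r = .7). The T3-minus-mean contrast equals T3 − T2 at r = .5 (.60 each) and is lower at r = .7 (.78 against .82). It still exceeds the 2-df test, which has about .54 at r = .5 and .74 to .75 at r = .7.

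**The case against.** The strongest reply is that the planned ANOVA is valid in this respect, matches the test behind the sample size, and already uses T1. That stands. Under equal correlation the interaction has the same noncentrality as the T3-minus-mean contrast and more power than a plain T3 − T2 change (62.9 against 60.2% at d = .8, r = .5). A reader might infer that the plan wastes the T1 session; the calculation does not support that.

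A reader might also credit the whole 7 to 14.5 points to T1, or call the change free. Neither is supported. Most of the gain comes from using 1 df and from ANCOVA, and T1 adds nothing beyond T2 adjustment if correlation decays over time. The two remedies are not equivalent either: their error variances differ, and ANCOVA can be biased if true baselines differ between groups formed by enrolment order. Pooling T1 and T2 also removes the control-period comparison from the main test, although the protocol gives it a purpose and it is the only check that the groups move in parallel before BFB.

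Finally, a reader might take the control-period sentence to mean testing (T3 − T2) − (T2 − T1). The plan states no such analysis, so its larger variance is no fault of the plan.

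What the reply does not remove is that no 1-df between-group test of T3 against baseline is named. Follow-up contrasts by group do not specify one.

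**Conclusion.** The point holds as one of efficiency and pre-specification, not of validity. Analysis A spends one of its two numerator df on a component that cannot contain a BFB effect. Under equal correlation of .5 to .8 and 40 against 10, a named 1-df contrast gains about 6 to 10 points, and two-baseline ANCOVA about 7 to 14.5, when planned power is roughly 30 to 85%. The gain falls to about 2 points near 96%.

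A reader might infer that the trial is short of power for HF because of this choice. At the effect implied by the stated N of 22 the gain is under 0.5 points, so the documents' own figures do not show that. The benefit lies with smaller effects, for which the plan gives no power. The correlations, the effects of .5 and .8 SD, and complete data are assumptions. Under AR(1) the contrast still beats the planned test but can fall slightly below T3 − T2.

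**What to change.** For outcomes measured at all three sessions:

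1. Pre-specify as the BFB test the 1-df group contrast of T3 minus the mean of T1 and T2, within the repeated-measures or mixed model.
2. Add ANCOVA of T3 on T1 and T2 as a sensitivity analysis, noting that baseline adjustment may be biased because groups follow enrolment order.
3. Keep the group × (T1–T2) component and the T1–T2 change as a separate pre-specified check, so that the control period keeps its protocol purpose.

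The cost is a few lines of SAP text, with no extra patients or visits. The downsides are reliance on a usable T1 and a possible small loss against T3 − T2 if correlation decays with time.

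### Analysis A does not name the between-group T2–T3 contrast as the test of biofeedback, and its follow-up contrasts can be read as separate tests in arms of 40 and 10

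*Combined protocol and SAP*

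**What the plan says.** For physiological and psychological outcomes alike, Analysis A (SAP, Statistical analyses) plans "An ANOVA to repeated measurement with an intra factor (measurement time: T1 / T2 / T3) and an inter factor (group: experimental / control"). It adds a t test before training, described as a "test for independent samples will be performed on the psychological scores collected in the second session (T2) to account for the initial level". It then states: "Contrasts will then be made by group on the scores in order to specify the effect of the condition".

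The Study protocol fixes the window in which training takes place: "The period (24 days) between the second session and the third session (T2-T3) will be considered as the intervention period", and "We will measure the parameters of interest before (T2) and at the end of the intervention period (T3"). Groups are formed by order of inclusion: "The first 40 participants (20 IBS / 20 PNES) will be included into the experimental group", and the last 10 form the untrained control group. The protocol also gives the T1–T2 period a role: "The larger BFB effects than the unspecific effects related to the spontaneous physiological and emotional variations will be verified through the control period".

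The Sample section says "The power analysis, for an ANOVA (repeated measures, within-between factors), was performed for an effect size" (partial eta squared) of .12 and power .95, with HF as main criterion. It does not name the interaction as the term powered.

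**The concern.** The planned ANOVA contains a between-group comparison of change, but the text does not say which term or contrast decides whether BFB worked. The sentence that specifies the condition effect can mean tests of change within each arm or comparisons between the arms. On the second meaning it still does not say whether the arms are compared on T3 scores or on T2–T3 change.

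These choices give different answers on the same data. With arms of 40 and 10, an identical change reaches significance far more easily in the trained arm, so a difference in significance can be taken for a difference in effect. The three-session interaction also reacts to differences between the groups that arise between T1 and T2, before anyone has trained. Such differences are possible because the first 40 and last 10 participants are not randomised. Leaving the choice until the data are seen could credit BFB with an effect that it did not have.

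**Working it through.** **Inputs.** From the documents: arms of 40 and 10 (Study protocol), alpha .05 (Statistical analyses), partial eta squared .12, power .95 and N = 22 (Sample). Assumed, because the documents give none: two-sided contrasts, correlation between sessions ρ = .5 or .7, compound symmetry unless stated, and the sizes of drift, divergence and effect. Two units are used. The SD of change equals √(2(1−ρ)) times the SD of score, which is 1.00 at ρ = .5 and 0.77 at ρ = .7.

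**1. The plan's sample size.** f² = .12/.88 = .136. For a 2-group × 3-time interaction, λ = f²·N·3/(1−ρ), with 2 and 2(N−2) df. At ρ = .5 and sphericity, N = 20 gives λ = 16.4 and power .944; N = 22 gives λ = 18.0 and power .964. The stated 22 is reproduced as the smallest equal-group N, so the sample size is consistent with the interaction.

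**2. Within-arm reading, no BFB effect.** Both arms change by d SD of change from T2 to T3. The power of a paired t test with n patients comes from the noncentral t with noncentrality d√n. The chance of significance in BFB only is power(40) × (1 − power(10)).

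| d | power, n = 40 | power, n = 10 | BFB only | control only | BFB only if 25/25 |
|---|---|---|---|---|---|
| 0.3 | .457 | .136 | 39% | 7% | 21% |
| 0.5 | .869 | .293 | 61% | 4% | 22% |
| 0.8 | .999 | .616 | 38% | 0.1% | 3% |

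The between-group difference in T2–T3 change rejects in 5% of trials in every row.

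**3. The two possible safeguards** (simulation, ρ = .5 and .7, 40,000 runs each).
- Counting the result only if the omnibus interaction is also significant: 2–3%.
- Requiring instead that T2–T3 change differs from T1–T2 change in the BFB arm: about 2% at each d if the drift is steady across sessions, but 15%, 30% and 31% at d = 0.3, 0.5 and 0.8 if it falls in T2–T3 alone.

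**4. The omnibus interaction, no BFB effect.** Let δ be the group difference at T1, T2 and T3 in SD of score. With 40·10/50 = 8, λ = 8·Σ(δⱼ − mean δ)²/(1−ρ) on 2 and 96 df. For δ = (0, .5, .5) the sum is .1667. Then λ = 2.67 at ρ = .5 (rejects 28%) and 4.44 at ρ = .7 (rejects 44%). The T2–T3 contrast has δ₃ − δ₂ = 0 and rejects 5%.

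**5. What the T2–T3 contrast costs.** λ = 8(δ₃ − δ₂)²/(2(1−ρ)) on 1 and 48 df. For a true effect δ = (0, 0, .8):

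| ρ | T2–T3 contrast | omnibus interaction |
|---|---|---|
| .5 | λ = 5.12, power .60 | λ = 6.83, power .63 |
| .7 | λ = 8.53, power .82 | λ = 11.38, power .85 |

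Under serial (AR(1)) correlation the order reverses (.60 against .54; .82 against .74). The 95% CI half-width is 2.011 × √(1/40 + 1/10) = 0.71 SD of change. If a 0.5 SD (of score) gap exists only at T2, δ = (0, .5, 0), the contrast rejects falsely in 28% (ρ = .5) to 43% (ρ = .7) of trials.

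**6. The T2 t test.** For an imbalance of 0.5 SD of score, λ = 8 × .25 = 2 on 1 and 48 df, so power is 28%. It covers the psychological scores only, not HF, and adjusts nothing.

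**The case against.** The best defence is that the plan already points to the right comparison. A group × time ANOVA yields the interaction by construction, and the sample size reproduces as that interaction. The contrasts come after the ANOVA, in an analysis described as staged, which is usual wording for follow-up of a significant term. The protocol sets T2 and T3 as the ends of the intervention period and says that BFB effects will be checked against the T1–T2 control period. A careful analyst could choose the T2–T3 group contrast unprompted.

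Much of this stands. A reader might infer that the contrasts will be run whatever the interaction shows, or that the SAP has committed itself to within-arm tests. The documents support neither: the first is inferred from silence, and the second is one reading of an ambiguous phrase. A reader might also take 61% as the trial's false-positive rate. It is not. It is the largest of the three rates shown, under an assumed shared drift, with neither safeguard applied. Once the control-period comparison is made, a large rate survives only if the drift falls mainly in T2–T3.

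The defence does not close the gap. Analysis A states an order, not a condition, and it does not write the control-period comparison as a test. Relying on the interaction instead brings in T1–T2 differences that precede training.

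**Conclusion.** The point holds as a failure to name the deciding test, and it should be fixed. Two routes that the text leaves open can credit BFB with an effect that it did not have. Separate within-arm tests do so in 39%, 61% and 38% of trials at 0.3, 0.5 and 0.8 SD of change, given equal T2–T3 change in both arms and neither safeguard. The omnibus interaction does so in 28–44% of trials, given a 0.5 SD (of score) divergence that arises by T2 and persists. The between-group T2–T3 contrast stays at about 5% in both settings. All drift and divergence sizes and both correlations are assumptions.

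Two further inferences would go too far. The plan does not lack a between-group comparison, since its model contains one. Nor is the omnibus test underpowered on the plan's own inputs: at 40/10 and ρ = .5, λ = .136 × 50 × 3/.5 × .64 = 26.2, giving power of 99.7%, where .64 = 4 × .8 × .2 allows for the unequal arms.

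**What to change.** Within the planned model, define the BFB effect on HF, and on the other outcomes measured at all three sessions, as one 1-df contrast: the T3−T2 change in the experimental group minus that in the control group, with a 95% CI. If the SAP's non-parametric route is taken, compare the same individual changes between groups. Label within-group contrasts descriptive. Do not present the T2 t test as adjustment for initial level.

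The protocol's comparison of T2–T3 with T1–T2 change can be kept as a supporting analysis. Two sensitivity analyses are optional: the group difference in T1–T2 change (28–43% power for a 0.5 SD of score divergence), and T3 minus the mean of T1 and T2. The latter rejects falsely in 13–18% of trials under the T2-only gap, against 28–43% for the main contrast.

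The cost is SAP wording; no new data are needed. The contrast gives up a little power to the omnibus test under compound symmetry, has a wide interval, and is sensitive to a gap present only at T2. It cannot remove bias from assigning the first 40 and last 10 participants by order of inclusion.
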